#### 14-Day Washout

1. Drugs with known pharmacologic activity at 5-HT4, 5-HT2b or 5-HT3 receptors (eg, cisapride, tegaserod, prucalopride, ondansetron, tropisetron, granisetron, dolasetron, mirtazapine)
2. Any of the following treatments either alone or in combination: plecanatide, lubiprostone, colchicine, linaclotide, and misoprostol
3. Prokinetic agents (eg, metoclopramide, itopride, domperidone)
4. Anticholinergic agents (eg, dicyclomine, flavoxate, scopolamine, hyoscyamine, propantheline, oxybutynin, tolterodine, solifenacin, darifenacin, trospium). (Note: inhaled ipratropium and tiotropium are permitted)
5. Bile acid sequestrants (eg, cholestyramine, colestipol)
6. Cholinomimetic agents (eg, bethanechol, pyridostigmine, tacrine, physostigmine). (Note: intraocular cholinomimetic agents such as pilocarpine are permitted)

7. Antipsychotic agents (eg, risperidone, haloperidol, droperidol, chlorpromazine, perphenazine, all phenothiazines, quetiapine, olanzapine, clozapine), unless the participant has been on a stable dose for 30 days before the Screening Visit (Visit 1) and plans to continue stable dosing for the duration of the study. (Note: paliperidone is permitted without restriction)
8. Antidepressants, unless the participant has been on a stable dose for 30 days before the Screening Visit (Visit 1) and plans to continue stable dosing for the duration of the trial. Specifically included are the following:
  - a. Tricyclic antidepressants (eg, amitriptyline, imipramine, nortriptyline)
  - b. Monoamine oxidase inhibitors (eg, furazolidone, isocarboxazid, pargyline, phenelzine, selegiline, tranylcypromine)
  - c. Selective serotonin reuptake inhibitors (eg, fluoxetine, sertraline, paroxetine, escitalopram, citalopram, vilazodone)
  - d. Serotonin-norepinephrine-reuptake inhibitors (eg, levomilnacipran, duloxetine, venlafaxine, desvenlafaxine succinate)
  - e. Other antidepressants (eg, trazodone, bupropion)
9. Calcium-channel blocker verapamil, unless the participant has been on a stable dose for 30 days before the Screening Visit (Visit 1) and plans to continue stable dosing for the duration of the study. (Note: all other calcium-channel blockers [eg, nifedipine, diltiazem, amlodipine, felodipine, nicardipine, nimodipine, nisoldipine] are permitted and may be used without restriction)
10. Oral and parenteral antibiotics; however, 1 standard regimen (up to 10 days) of oral antibiotics is permitted during the Study Intervention and Postintervention Periods
11. Any study intervention or imported drugs that have not been approved for human use
12. All narcotics (eg, tramadol, codeine, morphine, propoxyphene, loperamide, diphenoxylate, paregoric), either alone or in combination. Note: narcotics used as anesthesia for a colonoscopy require a 5-calendar day wash-out prior to the participant entering into the Preintervention Period. Dextromethorphan, the cough suppressant in many over-the-counter cold and cough medicines, is allowed
13. Any medicine taken for the purpose of losing weight (eg, orlistat, phentermine, phendimetrazine, diethylpropion, benzphetamine, sibutramine)
14. Any medication to treat attention-deficit/hyperactivity disorder, unless the participant has been on a stable dose for  $\geq 30$  days before the Screening Visit (Visit 1) and plans to continue stable dosing for the duration of the study

15. Any medicine that is known to cause diarrhea (eg, acarbose)
16. Proton pump inhibitors (eg, omeprazole, lansoprazole, esomeprazole, pantoprazole, rabeprazole), unless the participant has been on a stable dose for 30 days before the Screening Visit (Visit 1) and plans to continue stable dosing for the duration of the study
17. Other drugs such as barbiturates (eg, butalbital, phenobarbital) and chronic oral or parenteral glucocorticoids, which must be discontinued at least 3 months before screening; however, one 10-day course of oral or 1 injection of parenteral glucocorticoids is permitted during the Study Intervention and Postintervention Periods. Pregabalin is acceptable, provided the participant has been on a stable dose during the 30 days before the Screening Visit and plans to continue stable dosing throughout the study.

### 6.5.2. Rescue Medication

Rescue medication is not allowed on the day prior to Visit 3 (Randomization Visit), on the day of Visit 3, and the day following Visit 3.

In the United States and Canada, protocol-permitted rescue medication will be a choice of senna (oral) or bisacodyl (oral or rectal) that will be dispensed according to the SOA (Section 1.3).

Outside of the United States and Canada, protocol-permitted rescue medication will be a choice of senna (oral), bisacodyl (oral or rectal) or sodium picosulphate (oral) that will be dispensed according to the SOA (Section 1.3). Participants outside of the United States and Canada will have a choice of at least one of these medications. When there is more than one option available, the participants will choose rescue medication(s) at the Preintervention Visit (Visit 2) and study site staff will register the rescue medication in IWRS, where applicable. The study site must contact the IWRS (if applicable) at all subsequent study visits to obtain the protocol-permitted rescue medication to be dispensed to the participant at each visit as needed.

Rescue medication may be taken when at least 72 hours have passed since the participant's previous BM or when their symptoms become intolerable.

Where available, the participant may continue using their original selection received from the study site throughout the duration of the study or may switch to another protocol-permitted rescue medication in coordination with the site staff.

### 6.6. Dose Modification

For both FC and IBS-C participants, the investigator may allow a participant to stop taking study intervention for up to 3 days because of an intolerable AE. If the investigator believes that the participant is unable to resume dosing after 3 days or requires a suspension of dosing on more than 1 occasion, the investigator is required to contact the study physician to discuss the participant's continued participation in the study.

For IBS-C participants experiencing an intolerable AE that may be related to the use of linaclotide,

- those randomized to the 145 µg dose can be dose reduced in a double-blinded fashion to 72 µg linaclotide, and
- those randomized to the 290 µg dose can be dose reduced in a double-blinded fashion to 145 µg linaclotide during the course of the study at the investigator's discretion.

### **6.7. Intervention after the End of the Study**

Participants that complete LIN-MD-64 have the option to enroll into the open-label, long-term safety study, LIN-MD-66, if they meet the eligibility criteria. Participants will be considered to have completed LIN-MD-64 if he/she has completed 12 weeks of double-blind study intervention, the EOT visit (Visit 7), and the EOS visit (Visit 8). However, this EOS visit in LIN-MD-64 is not required for participants who enroll into the open-label, long-term safety study LIN-MD-66 prior to that visit.

## **7. Discontinuation of Study Intervention and Participant Discontinuation/Withdrawal**

### **7.1. Discontinuation of Study Intervention**

A premature discontinuation will occur when a participant who gave voluntary assent, and whose parent/guardian/LAR gave consent, ceases participation in the study, regardless of circumstances, before the completion of the protocol-defined study procedures.

Definitions of the standard terms that may lead to discontinuations are provided in [Appendix 5](#) (Section 10.5).

See the SoA for data to be collected at the time of intervention discontinuation and follow-up and for any further evaluations that need to be completed.

Reasons for discontinuation from the study intervention and/or the study may include the following commonly used or other acceptable terms:

Commonly Used Terms	Other Acceptable Terms
Adverse event	Death
Completed	Disease relapse
Lack of efficacy	Progressive disease
Lost to follow-up	Recovery
Other	Technical problems
Physician decision	Withdrawal by parent/guardian
Pregnancy	
Screen failure	
Site terminated by sponsor	
Study terminated by sponsor	
Withdrawal by subject	

### 7.1.1. Removal of Individual Participants from Therapy or Assessment

Participants **must** be prematurely discontinued from the study for reasons of safety including those who experience:

- An SAE considered by the investigator or the sponsor to be possibly related or related to study intervention,
- An AESI (evidence of significant volume depletion and/or significant electrolyte and/or ECG abnormalities that are considered by the investigator or sponsor to be related to diarrhea) related to the study intervention (ie, intervention-related AESIs) see Section 8.3.4,
- Pregnancy,
- The presence of intentional overdose or intentional misuse per investigator discretion,
- The occurrence of any other AE that in the opinion of the investigator or the sponsor is possibly related or related to the study intervention that represents a clinically significant safety risk to the participant

Participants **may** also be prematurely discontinued from the study for reasons of safety including those who experience:

- A vital sign, ECG, and/or laboratory abnormality judged to be clinically significant by the investigator and that in the opinion of the investigator or the sponsor is possibly related or related to the study intervention,
- An intolerable AE (defined as an AE that subjectively would cause a patient to consider study withdrawal), see Section 8.3

Additionally, discontinuation of study intervention for abnormal liver function should be considered by the investigator when a participant meets the criteria for Hy's law or the appearance of abnormal laboratory test results suggesting severe drug-induced liver injury (DILI), or if the investigator believes that it is in best interest of the participant (refer to [Appendix 9](#)).

All enrolled participants who prematurely discontinue from the study, regardless of cause, should be seen for the assessments to be completed at the EOT Visit. The EOT assessments are defined as completion of evaluations scheduled for all participants.

Participants who discontinue from the study and do not return to the study site for EOT Visit must be requested in writing to return to the study site for procedures required at the EOT Visit as defined in the SoA and return any unused study intervention. A copy of the letter, together with the source documentation, will be kept in the investigator's files. The reason for premature discontinuation from the study will be recorded on the Study Termination Page of the eCRF. Study site staff will be contacted by the sponsor after each premature discontinuation to ensure proper characterization of the reason for discontinuation is captured.

See the SoA for data to be collected at the time of study intervention discontinuation and follow-up and for any further evaluations that need to be completed.

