#### 8.2.4. Clinical Safety Laboratory Assessments

See Section 10.2 for the list of clinical laboratory tests to be performed and the SoA (Section 1.3) for the timing and frequency.

- At Screening (Visit 1), the investigator will assess the clinical significance of any values outside the reference ranges provided by the laboratory, and participants with abnormalities judged to be clinically significant will be excluded from the study.
- The investigator must review the laboratory reports, document this review, and record any clinically relevant changes occurring during the study in the AE section of the eCRF. The laboratory reports must be filed with the source documents. Clinically significant abnormal laboratory findings are those which are not associated with the underlying disease, unless judged by the investigator to be more severe than expected for the participant's condition.
- All laboratory tests with values considered clinically significant during participation in the study or within 30 days after the last dose of study intervention should be repeated until the values return to normal or baseline or are no longer considered clinically significant by the investigator or medical safety physician.
  - If such values do not return to normal/baseline within a period of time judged reasonable by the investigator, the etiology should be identified, and the sponsor notified.
  - All protocol-required laboratory assessments, as defined in Section 10.2, must be conducted in accordance with the SoA and the laboratory manual.
  - If laboratory values from non-protocol specified laboratory assessments performed at the institution's local laboratory require a change in participant management or are considered clinically significant by the investigator (eg, SAE or AE or dose modification), then the results must be recorded in the eCRF.
- Participants with clinically significant electrolyte abnormalities that are considered to be secondary to diarrhea (ie, an AESI) must be reported to the sponsor within 24 hours on an SAE form if considered to be serious. Non-serious events do not require submission on an SAE form; rather, these events only need to be entered into the eCRF (Section 10.3). If the AE is assessed as causally related to the use of study intervention, the participant should be discontinued from the study; however, the study physician and investigator may discuss individual participants and AEs to make this determination (Section 10.3).

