## 10.2. Appendix 2: Clinical Laboratory Tests

Blood and urine samples for clinical laboratory tests will be collected as detailed in the SoA (Section 1.3). During the Screening Period, the investigator will assess the clinical significance of any values that are outside the reference ranges provided by the central laboratory. Participants with abnormalities judged to be clinically significant will be excluded from the study.

Participants with clinically significant electrolyte abnormalities that are considered to be secondary to diarrhea (ie, an AESI) must be reported to the sponsor within 24 hours on an SAE form if considered to be serious. Non-serious events do not require submission on an SAE form; rather, these events only need to be entered into the eCRF (Section 10.3). If the AE is assessed as causally related to the use of study intervention, the participant should be discontinued from the study; however, the sponsor and investigator may discuss individual participants and AEs to make this determination.

Clinical laboratory levels that will be measured are summarized in Table 10-1.

The clinical significance of a positive urine drug screen will be assessed by the investigator. Participants will be excluded from study participation if urine drug screening results are positive for cocaine, barbiturates, opiates, or cannabinoids.

Serum pregnancy test (for female participants of childbearing potential) will be obtained at Screening (Visit 1) and a urine pregnancy test will be performed at the Randomization Visit (Visit 3) prior to dosing as specified in the SoA (Section 1.3) and during treatment at Week 4 (Visit 5), Week 8 (Visit 6) and Week 12/EOT (Visit 7). Positive results on the pregnancy test at Screening (Visit 1) and Randomization (Visit 3) will exclude participants from participating in the study. Positive pregnancy test results during the study intervention will result in participant termination from the study. Investigators must inquire at every study visit about the use of acceptable methods of contraception in participants of childbearing potential who are, or become, sexually active (see Inclusion Criterion 3.02), and perform a serum or urine pregnancy test if there is any question of noncompliance with contraception. Repeat pregnancy tests may be performed at the investigator's discretion at other times during the study.

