
Approval Date: 05-Jun-2020 15:39:03 (GMT)

If the AESI is assessed as causally related to the use of study intervention, the participant should be discontinued from the study (Section 10.5).

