#### **Reporting of Potential Hy's Law Cases**

Potential Hy's law cases are defined by biochemical test results of hepatocellular injury and impaired hepatic function. They are considered Adverse Events of Special Interest (AESIs) and should be evaluated and followed further (ie, close monitoring initiated) to determine whether these laboratory abnormalities are indicative of DILI. As indicated above, discontinuation of study intervention should also be considered. Criteria that identify a potential Hy's law case are as follows:

- ALT or AST  $\geq 3 \times$  ULN AND
- Total bilirubin  $\geq 2 \times$  ULN AND
- Alkaline phosphatase  $< 2 \times$  ULN

Sites must report every participant who meets the Hy's law criteria if this occurs within the time the participant signs the ICF until 30 days after the last dose of study intervention.

A laboratory alert for a potential DILI case will be sent immediately to the sponsor and investigators when the above criteria have been met, even if no clinical symptoms have been experienced. In addition, both an SAE and Adverse Event of Interest Abnormal Liver Function Reporting Form (GPSE-PVOPS-F-01-28) for all potential Hy's law DILI cases should be completed as soon as possible (within 24 hours of learning that a participant fulfills the potential Hy's law criteria) and submitted to the sponsor as noted in [Appendix 3](#). The eCRF pages associated with the potential Hy's law cases must be completed within 7 calendar days.

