6.4 Safety Population

The Safety Population will consist of all participants in the Randomized Population who receive at least 1 dose of double-blind study intervention.

Participants will be summarized according to the study intervention they actually received for all safety analysis variables/endpoints. If a participant received study intervention other than

randomized study intervention, actual study intervention received will be determined based on the study intervention received for the majority of the double-blind Study Intervention Period. If there is a tie, the higher dose will be considered the actual study intervention for that participant. This is also relevant for subjects who require dose de-escalation, which is allowed once per participant to ensure safety and tolerability for study subjects. The actual study intervention will be listed for the participants in the listing related to study intervention dosing information.

7 Participant Disposition

The number and percentage of participants in 3 study populations (Randomized, mITT, and Safety) will be summarized overall, by study intervention group, country, and study center; the number of participants screened will be summarized overall, only by country, and study center.

Screen-failure participants (ie, participants who are screened but do not enter into the Preintervention Period), participants ineligible for randomization (ie, participants who enter into the Preintervention Period but are not randomized at Visit 3, also labeled as preintervention failures), and the associated reasons for failure as recorded in the electronic case report forms (eCRF) will be tabulated overall for all screened participants.

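### Section 7.1.1 requires removal for every intervention-related AESI; Sections 8.2.3, 8.2.4 and Appendix 2 soften this to *should* with case-by-case discussion for ECG and electrolyte AESIs, and 10.3.1 says *should* for all

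*Protocol*

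**What the plan says.** Protocol Section 7.1.1 has two lists, one for events after which a participant *must* be discontinued and one for events after which a participant *may* be. An AESI "related to the study intervention (ie, intervention-related AESIs) see Section 8.3.4" is on the first list, with no exception attached.

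Three other places deal with the same events when they show up as an ECG or laboratory finding. Sections 8.2.3 (ECG abnormalities secondary to diarrhea) and 8.2.4 (electrolyte abnormalities secondary to diarrhea) both label the finding an AESI. Both say that, if it is causally related, "the participant should be discontinued from the study; however, the study physician and investigator may discuss individual participants and AEs to make this determination". Appendix 2 (Section 10.2) repeats the electrolyte rule and ends "however, the sponsor and investigator may discuss individual participants and AEs to make this determination".

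Section 10.3.1 covers AESIs of every type: "If the AESI is assessed as causally related to the use of study intervention, the participant should be discontinued from the study". It has no discussion clause.

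**The concern.** This is a stopping rule for children, and it should read the same wherever a site meets it. As written, a site that keeps a child with a related electrolyte or ECG AESI after discussion complies with 8.2.4 or 8.2.3 and breaches 7.1.1. Section 8 rules out waivers, so the breach cannot be excused as an agreed exception.

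The AESI category exists because of a recognized risk. Section 2.2.4 reports post-marketing cases in adults of severe diarrhea accompanied by syncope, low blood pressure and electrolyte disturbance. What is at stake is consistent handling of a child with a drug-related electrolyte or ECG abnormality during dosing.

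**Working it through.** There is no plan figure to reproduce. The check sets the texts side by side, then asks when the difference can matter and how often.

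**Step 1: the five statements.**

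| Protocol section | AESI types covered | Verb | Discussion clause | Refers reader to |
|---|---|---|---|---|
| 7.1.1 | all three | must | no | 8.3.4 (follow-up of AEs) |
| 8.2.3 | ECG | should | yes | 10.3 |
| 8.2.4 | electrolyte | should | yes | 10.3 |
| 10.2 (Appendix 2) | electrolyte | should | yes | 10.3 |
| 10.3.1 (Appendix 3) | all three | should | no | 10.5 (glossary of discontinuation terms) |

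The discussion clause reaches two of the three AESI types. For volume depletion, the only softer text is the *should* in 10.3.1. None of the four softer statements cites 7.1.1, so a site that starts from an abnormal potassium or ECG and follows the references is not led to *must*.

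**Step 2: what the discussion clause governs.** The sentence begins from an event already assessed as causally related, states that the participant should be discontinued, and then qualifies that with *however*. The natural reading is discretion over discontinuation. If the determination meant is causality, the exception disappears, but *must* against *should* remains.

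**Step 3: when the choice arises.**
- A serious related AESI is also a related SAE, which is a separate item on the *must* list in 7.1.1. The exposed cases are mainly non-serious ones.
- The Schedule of Activities (Section 1.3) has ECGs at Screening and end of treatment (EOT), and laboratory tests at Screening, Randomization and EOT. Section 10.10.3 places the first dose after the other Visit 3 assessments, so the Randomization sample is pre-dose. The EOT visit follows at least 84 days of dosing, or early discontinuation. No scheduled ECG or laboratory result therefore arrives while a child is still on drug.
- Unscheduled visits and additional tests are allowed (Section 1.3, footnote u; Appendix 2). Those are where a keep-or-remove decision can occur.

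**Step 4: expected number.** From Section 2.2.2, linaclotide-treated Phase 2 children number 116 + 16 + 74 + 8 = 214, with no AESIs in either study. The one-sided 95% upper bound is 1 − 0.05^(1/214) = 1.39%. Planned linaclotide participants here are 163 + 50 + 50 = 263.
- At the Phase 2 rate (assumption): 263 × 0.0139 = 3.7 children at most.
- If risk scales with 12 weeks against 4 (assumption): 263 × [1 − (1 − 0.0139)³] = 10.8 at most.

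These are ceilings for all AESIs, related or not and of every type. The number exposed to the wording conflict would be smaller.

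**The case against.** The strongest opposing case is that this is a drafting mismatch with little consequence. Much of that stands. Related serious events are covered by another mandatory item. Scheduled tests cannot create the dilemma. No AESI was seen in Phase 2. What does not fall away is that four current statements give a weaker rule than 7.1.1 for events in the same class.

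Several stronger readings are tempting, and the documents do not support them.

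- *Different people decide in different sections.* Section 8.2.4 names the study physician and Appendix 2 the sponsor. But Appendix 9 describes the study physician as the sponsor's, and for doubt about whether an AESI criterion is met, 8.3.1 sends the site to the sponsor while 10.3.1 sends it to the study physician. The labels are used interchangeably for one sponsor-side role.
- *Section 6.6 offers a way to keep the child.* It says "the investigator may allow a participant to stop taking study intervention for up to 3 days because of an intolerable AE" and, for IBS-C, "those randomized to the 290 µg dose can be dose reduced in a double-blinded fashion to 145 µg linaclotide". Its trigger is an intolerable AE, which 7.1.1 places on the *may* list, and nothing in 6.6 overrides the *must* list. A clarifying sentence is optional.
- *The conflict distorts safety reporting by dose.* Under Section 6.4 of the IBS-C SAP, "actual study intervention received will be determined based on the study intervention received for the majority of the double-blind Study Intervention Period". That rule can move any participant whose dose is reduced early, whatever the AE. It is a property of the SAP, and rewording the AESI rule would leave it unchanged.
- *Appendix 9 widens the AESI class to potential Hy's law cases.* It does say "They are considered Adverse Events of Special Interest (AESIs) and should be evaluated and followed further". But Section 8.3.7 requires these to be reported as SAEs, so a related case is already on the *must* list.

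**Conclusion.** The inconsistency is real and is in current text. Section 7.1.1 is mandatory for every intervention-related AESI. Sections 8.2.3, 8.2.4 and Appendix 2 are advisory with case-by-case discussion for ECG and electrolyte AESIs, and 10.3.1 is advisory for all AESIs. *Must* is probably the intended rule: the Amendment 1 summary records two criteria in 7.1.1 moving from *may* to *must* for participant safety. It does not name them, so this is supportive rather than conclusive.

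The practical gap is small: mainly non-serious, related ECG or electrolyte AESIs found on unscheduled testing during dosing. Few are expected, given 0 in 214. That reassurance assumes the Phase 2 experience carries over, although Phase 2 lasted 4 weeks and only 8 of those children, all aged 12 to 17, were assigned 290 µg. There is no effect on the efficacy analysis, because no endpoint, analysis population or test depends on this wording. A reader might infer that children have been or will be kept on drug wrongly; the documents show only that the text permits it. This is a point to consider, and it fits the next amendment.

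**What to change.** In 8.2.3, 8.2.4 and Appendix 2, replace the sentence with:

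> If the AESI is assessed as related to study intervention, the participant must be discontinued from the study (Section 7.1.1); the study physician and investigator may discuss the causality assessment.

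In 10.3.1, change *should* to *must* and refer the reader to 7.1.1 in place of the glossary in 10.5.

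Optionally, add to 6.6:

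> Interruption and dose reduction do not replace discontinuation for an intervention-related AESI.

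The cost is wording in four protocol sections, or five with the optional sentence, in one amendment that needs IRB/IEC approval. It adds no procedures, visits or participants and needs no SAP change.
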